14.1 Trial Management Group

The Trial Management Group under the chairmanship of the Chief Investigators ([name]) manages the trial on a day to day basis.

14.2 Trial Steering Committee

The Trial Steering Committee includes independent experts and monitors and supervises the progress of the trial towards its overall objectives including adherence to the protocol and patient safety.

Meetings are scheduled at 3, 6, 12, 24, and 30 months. Additional meetings will be scheduled should the need arise.

The steering committee includes the lead investigators and co-applicants:

[name]	Research dietitian	
[name]	Consultant Medical oncologist	
[name]	Consultant Medical oncologist	
[name]	Senior physiotherapist	
	B-AHEAD 3 Protocol v7.0 02/10/18 Page 27	

[name]	Senior lecturer / exercise specialist
[name]	Consultant Radiologist
[name]	Consultant Radiologist
[name]	Qualitative researcher
[name]	Senior statistician
[name]	Senior breast cancer research nurse
[name]	Senior breast cancer nurse

14.4 Data Monitoring Committee

We have recruited a Data Monitoring Committee (DMC): [name] (Medical Oncologist, Clatterbridge Centre for Oncology NHS Foundation Trust), [name], (Biostatistics at Queen Mary University of London), [name] (Lecturer, School of Health Sciences, University of Ulster)

The DMC will be responsible for safeguarding the interests of B-AHEAD 3 participants, assessing the safety of the interventions during the trial and for monitoring the overall progress and conduct of the clinical trial. The DMC will approve a Charter (stating frequency of meeting and terms of reference, etc) early on in the trial before the first planned meeting six months after randomisation of the first participant.

15. Data Handling and Record Keeping

All data will be kept strictly confidential according to Good Clinical Practice (GCP) Guidelines. All data will be stored by the University Hospital of South Manchester NHS Foundation Trust in a secure fashion for 20 years in accordance with the ICH GCP. Source data for the trial are pre chemo weights, CTCAE v 4 toxicity, Vibratip, quality of life data, treatment schedules and details of hospital admissions which will be stored at local hospitals on a trial case report form during the trial. These semi-anonymised forms (trial ID and patient initials) will be transferred to the B-AHEAD 3 researchers at MFT during the trial using secure methods i.e. nhs.net or fax. The B-AHEAD 3 researchers will also have source data; food diaries, physical activity questionnaires, muscle function tests, log of review calls from dietitian and physiotherapist and demographic information collected at baseline appointment. These data are stored in the participants' individual 'Participant Trial Files' kept in the B-AHEAD 3 research offices in the secure area of The Prevent Breast Cancer Research Unit. Prior to statistical analysis, all data will be entered from the Participant Trial Files to secure databases that will be anonymous. We have developed

an SOP for dealing with participant trial and medical records at MFT. In the other recruiting centres we require local PIs to be responsible for ensuring that their team meets local policies for documentation in both medical and trial records.

The CT scans used as part of routine care in the recruiting oncology centres will be transferred to The Nightingale Centre at MFT via the Image Exchange Portal. This is a secure method for transferring scan images that is widely used within the NHS.

16. Clinical Risk Assessment

16.1 Acting on low weight and BMI

The study team will collect weight from participants at their three weekly phone calls. If a participant has not recorded this information or if the study team have concerns about the validity of this information they will contact the relevant hospital team in order to create an accurate and complete record. The study team will calculate percentage weight change and alert the participant's medical oncologist and chemotherapy nurse if weight loss or gain exceeds 10% as this may require a reassessment of chemotherapy dose. BMI will be calculated and study dietitians will give advice on increasing calories if BMI goes below 19 kg/m².

Patients on the intermittent diet who achieve their healthy weight aim during the trial and are trying to maintain their weight should be encouraged to include 2 restricted days each week, whilst increasing amounts of the healthy Mediterranean diet (i.e. carbohydrate, protein and fat allowances) on the other 5 days.

16.2 Maintaining lean body mass

It is important that we ensure the safety of intermittent diet and resistance exercise interventions in these women with recurrent breast cancer, particularly to ensure they do not lose lean body (largely muscle) mass and that the interventions do not have adverse effects and increase toxicity from chemotherapy.

We only plan to include patients with ABC in the trial who are overweight or obese (BMI \geq 24 kg/m²) (~ 65% of our metastatic population). Such patients tend to have higher levels of adipose stores. Patients with raised adipose stores tend to lose body fat and preserve lean body mass. Unlike many advanced cancers at other sites (eg. lung) only a very small minority of advanced breast cancer patients have cachexia, and they will not be recruited to the study.

We are mindful however that some of our cohort may have reduced lean body mass at baseline despite being overweight with increased adiposity. Previously published data reported 20% of overweight patients receiving second line chemotherapy for metastatic breast cancer have low lean body mass (sarcopenia) (52). The trial includes ongoing assessment of CT scans at the frequency described in section 8.1.1 which are reported back to the trial team within 21 days. These CT scans will inform us if patients are reducing lean body mass and developing sarcopenia. In the unlikely event that this occurs the B-AHEAD 3 dietitian and physiotherapist will review the patient's advice and progress and provide appropriate diet and exercise advice to prevent further reductions. If this advice requires patients to stop following the diet patients would be censored as leaving the study.

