With the exception of these data the balance of evidence from the majority of animal and human studies indicates that higher protein intakes will not promote tumour growth amongst breast cancer patients. Reduced tumour growth and metastases with energy restriction has been achieved with maintained protein intake in the animal studies described above (11, 12, 41) (42, 43). Reduced relapse events amongst early breast cancer patients in the Women's Intervention Nutrition Study were achieved with a 10% energy restriction and a 50% reduction in fat intake and maintained protein intake (1g/kg body

weight) (OR 0.76 [95% CI = 0.60 to 0.98]) (3). Higher protein intakes are consistently linked with improved outcome amongst breast cancer patients (11, 12, 41), perhaps because they enable preservation of lean body mass. Trials of nutrition support have mainly found protein and branch chain amino acids stimulate muscle, liver and albumin synthesis and have minimal effects on tumour protein synthesis. Hence protein intake appears to favours host anabolism over tumour growth in cancer patients (53).

Our IER diet will therefore aim to maintain protein intake at 1 - 1.2 g per kg per day on restricted and unrestricted days. We anticipate the intermittent diet group will reduce energy intake by 30% overall and based on our previous data amongst patients with ABC the control group are likely to increase intake by 10% as is usually seen during treatment with chemotherapy (58). Thus overall our intervention group will have a 40% lower energy intake than our control group.

2.5 The importance of maintaining lean body mass in patients with ABC and rationale for the resistance exercise intervention

Recent data from Canada using CT scans to evaluate body compartments indicate 25% of patients with ABC (20% of the overweight and obese patients) have reduced lean body mass (sarcopenia) at the initiation of chemotherapy, and that chemotherapy toxicity and poorer outcome is specifically related to reduced lean body mass and not fat mass or BMI (52, 59). Likewise Aslani et al found reduced body nitrogen to be a key predictor of neutropenia with CMF chemotherapy amongst patients with early and ABC (60)

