5.1 Primary objective

Progression free survival (PFS), i.e. the time from randomisation to disease progression or death between the intervention and control group using standard RECIST criteria (Response Evaluation Criteria in Solid Tumors 1.1).

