6.1 Study design

This study will compare PFS amongst 134 overweight women (BMI \geq 24 kg/m²) commencing chemotherapy who are randomised to:

1. Intervention group: Advised to follow an intermittent energy restricted diet and undertake resistance exercise.

2. Control group: Advised to undertake resistance exercise only (and to follow their normal diet).

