8.2.2 Menstrual cycle

Pre-menopausal women in both diet groups ($\sim 10-20\%$ of the cohort) will be asked to complete a diary sheet of their menstrual cycle throughout the study. This will inform whether women are experiencing chemotherapy associated ammenorhea, which can be a factor in chemotherapy associated weight gain.

8.2.3 Sub-study 2: Qualitative evaluation of the weight loss / lifestyle programme in the energy restriction and resistance exercise only groups.

We are proposing to include a small in depth qualitative study amongst a sub set of participants to assess the acceptability of the intervention and IER diet amongst women with metastatic breast cancer. This sub study will be submitted as a future application to ethics.

9. Criteria for discontinuation of participants in the trial

The energy restriction and exercise interventions will extend until the first disease progression after commencement of study chemotherapy, even if chemotherapy had been stopped due to toxicity or completion of planned treatment (unless excluded by progression of bone metastases, see section 7.3.5). The average chemotherapy period of treatment is projected to be 5.4 months. The longest treatment period is predicted to be two years. We plan to censor patients in the study once the final recruited patient has been in the trial for 12 months.

Ongoing assessment of CT scans as per frequency described in section 8.1.1 (reported back within 21 days) will inform us if patients are experiencing reductions in lean body mass and developing sarcopenia. Sarcopenia is defined using the cut off point for lumbar skeletal muscle index of <38.5 $\rm cm^2/m^2$ for women (96). In the unlikely event that this occur the B-AHEAD 3 dietitian and physiotherapist will review the patient's advice and progress and provide appropriate diet and exercise advice to prevent further reductions. If this advice requires patients to stop following the diet their data will still be used in the primary analysis which is on an Intent To Treat (ITT) basis.

10. Statistical Considerations

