16.6 Generic Risk Assessment

Hazards to patients, study and organisation have been perfomed for the B-AHEAD 3 trial and have been considered low risk.

17. Predicted/possible deviations from the protocol and adverse events

The following is a list of possible/predicted deviations from the protocol and adverse events that would not require reporting to the sponsor or ethics committee:

Deviation / adverse event	Action
The participant does not receive chemotherapy once randomised	Participant is withdrawn from the study
Chemotherapy regimen is not given according to initial schedule, e.g. if one or more cycles are delayed for medical reasons	Dates of chemotherapy cycles are documented in participant's study file. Participant remains on study.
Research blood samples cannot be taken	See Blood Sampling SOP (Appendix 6). Participant is encouraged to stay on study.
Participant does not (fully) complete required food diaries	Participant is encouraged to remain on study. Food diary checked through with participant and more detail added if possible. Participant is encouraged to complete next food diary fully, if applicable. A diet history can be taken by BAHEAD 3 dietitians to describe the normal dietary intake.
Participant cannot adhere to or does not wish to adhere to allocated diet and/or exercise plan	Participant will be encouraged to remain on study as they are providing very useful information to the study team. They will be encouraged to stick to their allocated diet/exercise plan as best as they can. Researcher will document reported adherence and reasons for not following allocated diet/exercise plan in participant's study file. Diet/exercise plan will be adapted to patient's requirements if possible and adaptations will be recorded.
One or more chemotherapy treatments are delayed and toxicity scales cannot be completed for last 3 weeks.	Scales to be completed at next chemotherapy treatment and participant encouraged to give answers based on how they were feeling in the three weeks after last chemotherapy.

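### Sections 9 and 16.2 give opposite rules for women who must stop the diet because of muscle loss; if 16.2 were applied, PFS would be censored in the diet arm only

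*Protocol*

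**What the plan says.** Sections 9 and 16.2 follow the same path. Routine CT shows falling lean mass or sarcopenia, the dietitian and physiotherapist review the woman's advice, and that advice may mean giving up the diet. They then part:

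- **Section 9:** "their data will still be used in the primary analysis which is on an Intent To Treat (ITT) basis".
- **Section 16.2:** "If this advice requires patients to stop following the diet patients would be censored as leaving the study".

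Other places bear on which rule fits the rest of the plan:

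- Section 5.1 defines PFS as "the time from randomisation to disease progression or death". Stopping the diet is not part of it.
- Section 7.4 names two ways of leaving the study, the woman's own request and disease progression, and provides for consent to continued review of records and CT scans afterwards.
- Section 7.3.4 keeps CT monitoring going to progression even for women who decline all further contact after chemotherapy ends.
- Section 7.3.5 keeps study assessments going for women who must stop the exercises because of bone metastases.
- Section 17 says of a woman who cannot or will not follow her allocated plan: "Participant will be encouraged to remain on study as they are providing very useful information to the study team".
- Section 6.1 gives the trial diet to the intervention group only.
- Section 2.5 reports that "chemotherapy toxicity and poorer outcome is specifically related to reduced lean body mass and not fat mass or BMI".

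**The concern.** Censoring a woman when she stops her allocated intervention is not an intention-to-treat analysis, so the two sentences cannot be read together as keeping her data up to the censoring date. Staff following 16.2 and staff following 9 could handle the same woman's primary endpoint in opposite ways, each with support in the protocol.

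The 16.2 rule also has a direction. The control arm has no trial diet to stop, so only the diet arm can be censored by it. The trigger is loss of lean mass, which the protocol ties to poorer outcome. If that link holds for loss during treatment, women with a worse outlook would leave the diet arm's risk set while comparable women stayed in the control arm. The comparison would then tilt towards the diet. The decision to advise stopping also lies with staff who deliver the diet and know the allocation, whereas section 8.1.1 chose central blinded reading of PFS for its impartiality.

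At stake is a screening result, tested at a one-sided 20% level, that is meant to decide whether a phase III trial follows.

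**Working it through.** **1. The plan's own figures (section 10.1).** Inputs: hazard ratio 0.65, power 90%, one-sided 20%, control PFS 5.4 months (taken as a median), 15 months' accrual plus 15 months' follow-up, 15% dropout.

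- Events: 4(z₀.₈₀ + z₀.₉₀)² / (ln 0.65)² = 4(0.842 + 1.282)² / (−0.431)² = 97.2, so 98. Stated: 98.
- Patients: with exponential PFS and uniform accrual, the event probability per arm is 1 − [e^(−15λ) − e^(−30λ)] / (15λ), where λ = ln 2 / median. This is 0.935 for a median of 5.4 and 0.837 for 5.4/0.65 = 8.3 months, mean 0.886. Then 98/0.886 = 110.6, so 111. Stated: 114, within 3%.
- Dropout: 114/0.85 = 134.1. Stated: 134.

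The sample size is sound, and this point does not rest on it.

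**2. What the 16.2 rule would do with no true effect.**

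Taken from the protocol:
- 5.4-month control PFS and the accrual and follow-up times.
- 57 women per arm (114/2).
- A first muscle reading at about 12 weeks (section 8.1.1: scans 9–12 weekly), that is 84/30.4 ≈ 2.8 months.

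Assumed, because the protocol gives no figure:
- The share of women affected, equal in both arms.
- The multiple by which their hazard exceeds that of other women.
- That every affected woman in the diet arm who is event-free at 2.8 months is censored then.

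The analysis is a Cox model with treatment only and a one-sided 20% Wald test, in 8,000 simulated trials per setting. The simulation error is about √(0.2 × 0.8/8000) = 0.4 percentage points. Large-sample hazard ratios use 300,000 women per arm.

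| Share affected | Hazard multiple | Large-sample HR under 16.2 (true 1.00) | False-positive rate, section 9 rule | False-positive rate, 16.2 rule |
|---|---|---|---|---|
| 5% | 2 | 0.99 | 20.0% | 22.0% |
| 10% | 2 | 0.98 | 20.2% | 24.2% |
| 20% | 2 | 0.96 | 20.1% | 28.4% |
| 10% | 3 | 0.97 | 20.2% | 23.6% |
| 20% | 3 | 0.95 | 19.8% | 26.2% |
| 5–20% | 1 | 1.00 | – | – |

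A repeat run gave about 21% with 2% affected at twice the hazard. It gave 20% with 20% affected and no prognostic link. Varying the design (57 or 67 per arm, censoring at 2.5 or 2.8 months) gives, at twice the hazard, about 21–22% for 2–5% affected, 23–25% for 10% and 28–31% for 20%.

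**3. A check by hand.** Control hazard is ln 2/5.4 = 0.128 per month. At twice that, the share event-free at 2.8 months is e^(−0.128 × 2 × 2.8) = 0.49. With 20% affected, 57 × 0.20 × 0.49 ≈ 5.6 women are censored, which matches the simulated loss of events (108.0 to 102.5). With 5% affected it is 57 × 0.05 × 0.49 ≈ 1.4 women. At three times the hazard only e^(−0.128 × 3 × 2.8) = 0.34 remain event-free. Fewer are left to censor, so tripling is no worse than doubling.

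**4. Under the planned effect.** With a true HR of 0.65 and 20% affected, the large-sample estimate without censoring is 0.66–0.68 at two to three times the hazard. Under 16.2 it is 0.62. Loss of power is minor: if all 10 or so events in 20% of the diet arm were lost (98 × 0.5 × 0.2 = 9.8), power would still be 88%.

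**The case against.** The strongest reply is that section 9 already settles the analysis. It is the only place that names the primary analysis for this event. Section 16.2 sits under clinical risk assessment and mentions neither PFS nor the primary analysis. Sections 5.1, 7.3.4, 7.4 and 17 all fit section 9. This stands to a large degree: it makes 16.2 the outlier and makes the bias conditional. It does not remove the conflict, because 16.2 uses the language of censoring and also tells staff that the woman leaves the study, which affects what is collected as well as how it is analysed.

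Three stronger readings are tempting, and the documents do not support them.

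- **That PFS will be informatively censored.** This follows only if 16.2 is the rule applied. It also needs on-treatment muscle loss to predict progression, whereas the evidence in section 2.5 concerns lean mass when chemotherapy starts.
- **That a fifth of the diet arm would be censored.** The 20% in section 16.2 is the share of overweight patients who have low lean mass. It is not the rate of losing muscle during the trial, and still less the rate of being advised to stop the diet. Sections 9 and 16.2 call even the muscle loss unlikely, so the low end of the range is the case the protocol describes.
- **That section 17 breaks intention to treat as well**, by withdrawing a woman when "The participant does not receive chemotherapy once randomised". That rule applies to both arms and does not say that she is left out of the analysis, so it is not part of this point.

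**Conclusion.** The contradiction is explicit and bears on the primary endpoint, so the two sections must be reconciled. The harm is conditional: it arises only if 16.2 is followed and if the women concerned progress faster than others. Its direction would then favour the diet.

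The size is not in the documents. On the assumed doubling of hazard, the false-positive rate moves from 20% by one or two points if 2–5% of women are affected, and by eight to eleven points if 20% are. With no prognostic link it does not move. Since the protocol expects the event to be rare, a small effect is the more likely one. The case for correction rests on the conflicting rules and on the one-sided nature of the 16.2 rule, not on a large expected bias. Leaving the choice until outcome data are known would also expose the primary result to challenge.

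**What to change.** Replace the censoring sentence in section 16.2 with the section 9 analysis rule. Suggested wording: women who stop the diet for this reason continue to be followed by routine CT for PFS, and for survival, and are analysed in their randomised arm without censoring at the time the diet is stopped. Any censoring rules in the SAP should agree.

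This settles follow-up and analysis only. It says nothing on whether or when a woman should stop the diet.

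The cost is one sentence in a protocol amendment. The scans are routine care and already go to the coordinating centre (section 15), and the 98 events, 114 and 134 patients are unchanged.

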7.3.3 Monitoring weight

All patients will have their weight monitored at each chemotherapy cycle in their chemotherapy unit. This will allow us to make any necessary modifications to their dietary prescription if patients are losing too much weight (see section 16.1 'Acting on low weight and BMI'). A change in weight by - 10% alongside a grade ≥ 2 toxicity (as per section 6.4) will be communicated to the patient's medical oncologist so they can consider whether they wish to adjust the chemotherapy dose, which are dosed according to body weight and body surface area (see section 6.4 'Procedures for during and end of the study'). Patients in Group 1 will be provided with a diary to record their weight and waist.

7.3.4 Monitoring after discontinuation of chemotherapy due to excess toxicity or at the end of planned treatment

Participants will be offered three options at this point as they will no longer be having visits to their chemotherapy hospital at each cycle:

- 1. Continue with B AHEAD 3 phone calls from the research dietitian/ physiotherapist and attend for study assessments at chemotherapy centre around every 8-12 weeks (these appointments will hopefully coincide with visits to the centre for CT scans or clinic appointments)
- Don't attend for any more study assessments with research nurses, but continue with phone calls from B-AHEAD 3 research dietitian/ physiotherapist until CT scans show tumour progression
- 3. Don't attend for any more study assessments with research nurses, no more phone calls from B-AHEAD 3 study team CT scans will continue to be monitored until tumour progression

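### Sections 9 and 16.2 give opposite PFS data rules for women advised off the diet for lean-mass loss; following 16.2 would censor in the diet arm only, plausibly in its favour

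*Protocol*

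**What the plan says.** Section 9 (criteria for discontinuation) and section 16.2 (maintaining lean body mass) describe one sequence in nearly the same terms: a routine CT shows falling lean mass or sarcopenia, the dietitian and physiotherapist review the woman's advice, and that advice may mean stopping the diet. They then part.

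- Section 9: "their data will still be used in the primary analysis which is on an Intent To Treat (ITT) basis".
- Section 16.2: "If this advice requires patients to stop following the diet patients would be censored as leaving the study".

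Other parts of the protocol bear on which rule fits:

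- Section 5.1 defines the primary endpoint as "the time from randomisation to disease progression or death between the intervention and control group". Stopping the diet is neither an event nor a stated reason for censoring.
- Section 7.4 gives two reasons for leaving the study: the patient's request and disease progression. It also provides for asking verbal consent to go on reviewing records and CT scans after a woman leaves.
- Section 7.3.4 covers women who finish chemotherapy and want no further study contact. Even for them, "CT scans will continue to be monitored until tumour progression".
- Section 6.1 describes the comparator: "Control group: Advised to undertake resistance exercise only (and to follow their normal diet".
- Section 2.5 reports that "chemotherapy toxicity and poorer outcome is specifically related to reduced lean body mass and not fat mass or BMI".

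**The concern.** A censoring rule for the primary endpoint has to be single and fixed in advance. Here the protocol holds two, and the choice between them could be made after results are known.

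The 16.2 rule is also the wrong one for an intention-to-treat comparison of PFS. Lean mass is read from CT in both arms, but a control woman with the same scan has no study diet to stop, so she is followed to progression while her counterpart in the diet arm is cut off. If women losing lean mass progress sooner than the rest, as the protocol's own background suggests, some of the diet arm's earlier progressions disappear and the diet looks better than it is. The decision to stop is made by the dietitian and physiotherapist, who are not among the endpoint assessors that section 6.5 lists as blinded.

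**Working it through.** **The two rules against the rest of the protocol**

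| Source | Situation | Rule |
|---|---|---|
| Section 9 | Advised off the diet for lean-mass loss | Kept in the ITT primary analysis |
| Section 16.2 | The same | Censored as leaving the study |
| Section 5.1 | PFS definition | Runs to progression or death |
| Section 7.4 | Reasons for leaving | Own request or progression |
| Section 7.3.5 | All study exercise has to stop | Study assessments continue |
| Section 7.3.4 | No study contact after chemotherapy | CT followed to progression |

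Section 16.2 is the outlier. Reading section 9 as meaning that data are used up to a censoring date does not reconcile the two, because an ITT analysis of PFS does not end when an intervention ends.

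**The design figure (section 10.1)**

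Inputs: hazard ratio 0.65, power 90%, one-sided significance 20%; equal allocation is assumed. By Schoenfeld's formula, events = 4(z₀.₈₀ + z₀.₉₀)² / (ln 0.65)² = 4 × (0.8416 + 1.2816)² / 0.1856 ≈ 97.2, which rounds up to the stated 98. Power at 98 events is 0.902.

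**Illustration of the 16.2 rule**

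From the protocol: 114 patients, control PFS 5.4 months (taken as a median), 15 months' accrual plus 15 months' follow-up, one-sided 20% test.

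Assumed, not in the documents:

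- 20% of women in each arm are prone to low lean mass. The figure is borrowed from section 16.2, where it is a published prevalence.
- Their progression hazard is k times that of the others, with k = 1.5, 2 or 2.5.
- A share c of the prone women in the diet arm who are still progression-free at a 2.5-month scan is censored there.

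The average hazard is held at ln 2 / 5.4 = 0.1284 per month, so the base hazard is 0.1284 / (0.8 + 0.2k). For k = 2 the base is 0.1070 and the prone hazard 0.2139. Of the 57 × 0.20 = 11.4 prone women expected in the diet arm, 11.4 × exp(−0.2139 × 2.5) = 6.7 would be censored if c = 1, and about 0.7 if c = 0.1.

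Results with no true diet effect (Cox hazard ratio, one-sided log-rank test; 4,000 simulated trials per cell, 8,000 for the c = 0.1 row):

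| Share censored, c | HR (k = 1.5 / 2 / 2.5) | False-positive rate |
|---|---|---|
| 0.1 | 0.99 to 1.00 | 0.20 to 0.21 |
| 0.25 | 0.993 / 0.991 / 0.981 | 0.214 / 0.207 / 0.232 |
| 0.5 | 0.974 / 0.974 / 0.972 | 0.237 / 0.239 / 0.244 |
| 1 | 0.955 / 0.939 / 0.931 | 0.264 / 0.300 / 0.317 |

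The same trials analysed by ITT give a hazard ratio of about 1.00 and a false-positive rate of 0.186 to 0.208. Simulation error is about √(0.2 × 0.8 / 4000) = 0.006, so the rows for c = 0.1 and 0.25 are barely distinguishable from nominal. With k = 1 the hazard ratio stays at about 1.00 and the rate at 0.194 to 0.197: events are lost, but there is no bias. With 12 months' follow-up instead of 15, censoring all prone women gives hazard ratios of 0.959 / 0.937 / 0.935 and rates of 0.267 / 0.293 / 0.306, much the same.

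**The case against.** The strongest reply concerns size. Section 16.2 says: "Previously published data reported 20% of overweight patients receiving second line chemotherapy for metastatic breast cancer have low lean body mass (sarcopenia) (52". That is a published prevalence, cited to show that some women may have low lean mass at baseline. A reader might take it as the share who will be told to stop the diet, and so infer an inflated error rate of around 30%. The protocol does not support that. Both sections call the event unlikely, the first response is further diet and exercise advice, and stopping the diet is a later, conditional step with no rate given. This part of the objection stands: small stopping shares are equally compatible with the text, and they do almost nothing to the result.

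Three other strong readings also go too far.

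- That these women are removed from the analysis. Censoring keeps all their time and events up to the stop, and a progression found on the same scan can still count.
- That their follow-up ends. Section 7.4 allows CT and records review after leaving, with consent, and section 8.1.2 provides six-monthly notes checks for survival. The dates may therefore exist, but 16.2 would still leave them out of PFS.
- That section 17 contradicts 16.2 outright. It says "Participant will be encouraged to remain on study as they are providing very useful information to the study team", but of women who cannot or do not wish to adhere, not of a stop advised by the team. It is supporting context only.

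Finally, section 2.5 concerns low lean mass at the start of chemotherapy, whereas the rule concerns loss during it. Informative censoring is therefore plausible rather than shown.

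None of this removes the contradiction. Both sentences are current text on the primary endpoint.

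**Conclusion.** The concern holds as a contradiction between sections 9 and 16.2, with 16.2 wrong as written for an ITT analysis of PFS. Applied to PFS, it would censor in one arm only, and on the protocol's own prognostic premise the direction favours the diet.

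The size cannot be fixed from the documents. Under the stated assumptions it runs from negligible (fewer than one woman censored) to a null hazard ratio of about 0.93 with a false-positive rate of up to 32% (about six to seven women censored). It is nil if lean-mass loss carries no excess hazard. The case for correcting it rests on two incompatible rules for the primary endpoint, not on the upper end of that range.

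**What to change.** Replace the last sentence of section 16.2 with the section 9 rule, stated in full:

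- Stopping the diet on the team's advice is neither leaving the study nor a reason to censor PFS.
- CT, PFS, overall survival and safety follow-up continue to progression or death unless the woman withdraws consent, with records and CT review after leaving as section 7.4 already provides. A woman's right to leave at her own request is unchanged.
- She is analysed in her allocated arm.
- The date and reason for stopping the diet are recorded.
- Any analysis that censors at diet stop is labelled a sensitivity analysis.

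The cost is one sentence in the next amendment and a date and reason field on the case report form. The 98 events, 114 patients and 134 to be recruited do not change. When the diet should be stopped is a clinical matter and is not addressed here.
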